4. STUDY DESIGN

This is a prospective, observational, noninterventional cohort study designed to collect clinical information and specimens to evaluate the innate and adaptive immune responses from up to 1,000 study participants. Both males and females will be screened for study interest and eligibility and enrolled, adults ≥ 18 years of age and children < 18 years of age. Two types of participants will be recruited:

- Group 1: Patients with confirmed or suspected Pathogen “X” infection, and
- Group 2: Close contacts of patients with confirmed and/or suspected Pathogen “X” infection enrolled in Group 1.

The study will ensure enrollment of patients that have clinical symptoms representative of the disease spectrum.

Group 1

Baseline data will be collected from participants with confirmed or suspected Pathogen “X” infection including demographics/sociodemographics, medical history, exposure history, medications, signs/symptoms and symptom onset date to determine the days post-illness onset (DPO). Specimens will be collected from body compartment specific to Pathogen “X”. Specimens may include whole blood, serum, urine, saliva, stool or other body fluids as available (e.g., semen, vaginal secretions, breast milk) depending on the specifics of Pathogen “X”. Specimens may be salvaged if available from standard of care testing. Clinical information and specimens will be collected at enrollment and then at an interval determined by the biologic characteristics after enrollment (up to 12 months). See Section 6 Study Procedures/Evaluations.

The association between age, severity of illness, and duration of illness on Pathogen “X” immune responses will also be explored.

An optional study visit will be conducted between DPO 30 and 90 in adult participants from Group 1 who volunteer to undergo leukapheresis. Leukocytes will be selectively harvested; red cells and other blood components will be returned to the patient. Participation will be offered to all patients and volunteers will be accepted until the spots are filled. In a typical 1½ to 3-hour leukapheresis procedure, approximately 5×10^8 to 1×10^{10} cells can be isolated with only minimal loss of red blood cells. No sedation is required. The procedure will be done by trained staff at the study site and will be done using devices and procedures that conform to standard guidelines and SOPs.

Identification of close contacts will take place as soon as possible after Group 1 participants are enrolled.

Group 2

Close contacts, both symptomatic and asymptomatic, will be systematically identified, approached, consented, and enrolled into Group 2 (both children and adults) as soon as possible after their confirmed and/or suspected Pathogen “X” infected contact was enrolled.

Baseline data will be collected from Group 2 participants including demographics/ sociodemographics, medical history, exposure history, medications, and signs/symptoms. Specimens will be collected from body compartment specific to Pathogen “X”. Specimens may include whole blood, serum, urine, saliva, stool or other body fluids as available (e.g., semen, vaginal secretions, breast milk), depending on the specifics of Pathogen “X”. Clinical information and specimens will be collected at enrollment and then at an interval determined by the biologic characteristics after enrollment (up to 12 months). See Section 6 Study Procedures/Evaluations.

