5. STUDY POPULATION

5.1 Selection of the Study Population

Up to 1,000 male and female participants, adults ≥ 18 years of age and children < 18 years of age, will be screened to enroll participants who meet all eligibility criteria and agree to participate.

Patients will be recruited from 10 VTEU sites and/or their sub-sites. Sites can enroll from either outpatient or inpatient sites, or both. Enrollment will be stratified by disease severity or other major categories of disease presentation as applicable. Pregnant women will not be excluded from enrollment. Blood collection volumes will be adjusted accordingly for these participants. There will not be a required sample size for this population. As this study is a descriptive study, sample size is based on feasibility instead of power for hypothesis testing.

- Group 1: Patients with confirmed or suspected Pathogen “X” infection, and
- Group 2: Close contacts of patients with confirmed and/or suspected Pathogen “X” infection enrolled in Group 1.

A subset of 10-20 adult volunteers from Group 1 will undergo leukapheresis during follow-up to compare immunological responses in those with variable severity and also to allow future comparisons with those receiving Pathogen “X” vaccines (enrolled in other studies). Study staff will inform potential participants/legally authorized representatives (LAR) of the study, obtain informed consent, and determine study eligibility. Individuals who meet all study eligibility criteria and agree to participate will be enrolled.

Usual clinical management at VTEU outpatient or inpatient sites, including standard medical care and standard therapy, will not be modified because of the study. All participants will receive appropriate treatment for Pathogen “X” that is accepted by medical experts as standard of care for the specific institution and is widely used by healthcare professionals.

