5.2.2 Leukapheresis Inclusion Criteria

A subject must meet all the following criteria to be eligible for leukapheresis:

- Written informed consent for leukapheresis is provided.
- Age ≥ 18 years old.
- Weight ≥ 110 pounds.
- Screening laboratory (e.g., Hgb) and clinical (e.g., pulse, blood pressure) evaluations are within acceptable normal reference ranges at the site where the leukapheresis procedure will be performed.
- Negative urine or serum pregnancy test within 48 hours of the leukapheresis procedure for women of childbearing potential.
- Adequate bilateral antecubital venous access.
- No use of blood thinners, aspirin or NSAIDs at least 5 days before the leukapheresis procedure.
- Must be an outpatient at time of leukapheresis procedure.
- The investigator deems the participant is medically stable to undergo the leukapheresis procedure.

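### The leukapheresis subset is meant partly to compare severities, but its 10-20 places are filled in order of volunteering with no severity element, so it may hold too few formerly severe participants

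*Protocol*

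**What the plan says.** - **Purpose and size (Protocol Section 5.1).** "A subset of 10-20 adult volunteers from Group 1 will undergo leukapheresis during follow-up to compare immunological responses in those with variable severity". A second purpose is later comparison with vaccine recipients from other studies. Table 1 in Section 3.1 lists leukapheresis under an exploratory specimen-bank objective and describes the donors as selected.
- **Filling rule (Section 4, Group 1).** Every patient is offered the procedure, and "volunteers will be accepted until the spots are filled".
- **Eligibility (Section 5.2.2).** "Must be an outpatient at time of leukapheresis procedure". Also: "Screening laboratory (e.g., Hgb) and clinical (e.g., pulse, blood pressure) evaluations are within acceptable normal reference ranges"; "The investigator deems the participant is medically stable to undergo the leukapheresis procedure"; "No use of blood thinners, aspirin or NSAIDs at least 5 days before the leukapheresis procedure".
- **Timing (Sections 4 and 6.1.3).** The visit falls between 30 and 90 days after the participant's own illness onset (DPO 30-90).
- **Severity (Section 7.1).** The primary analysis classes Group 1 by the worst level of care received: ICU, hospital without ICU, or never hospitalized.
- **Stratification (Protocol Summary and Section 5.1).** Enrollment into the study is stratified by severity or other presentation categories, as applicable. Nothing similar is stated for the leukapheresis subset.

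**The concern.** A subset collected to compare severities needs some members at each severity level, or at least at two of them. Table 1 implies that donors are chosen, but no section says on what basis, and the only filling rule stated takes whoever volunteers until the places run out. The severity mix is therefore left to chance and to whatever shapes the pool of eligible volunteers.

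That pool is probably tilted towards milder illness. Being out of hospital, having normal screening values, being judged stable and being off blood thinners between DPO 30 and 90 are all plausibly harder to meet after severe illness. If the places fill with few formerly severe participants, the comparison named in Section 5.1 cannot be made from this subset even descriptively, and no later analysis plan can recover cells that were never collected.

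**Working it through.** The protocol derives no figure for the subset beyond its size, so there is nothing of its own to reproduce. The check asks how likely a near-empty severe group is under the stated rule.

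**Inputs**
- Places: n = 10 and n = 20 (Section 5.1).
- Severe share p among eligible volunteers: not in the protocol. Assumed values are 5%, 10%, 20% and 33%. The last is the favorable case in which three care levels are equally represented among volunteers.
- Severe here means former ICU care, the top level in Section 7.1.

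**Step 1: chance of few severe participants.** If volunteers arrive independently, the number of severe participants is binomial:

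P(none) = (1 − p)^n, and P(at most one) = (1 − p)^n + n·p·(1 − p)^(n−1).

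Example, n = 10 and p = 0.10: 0.9^10 = 0.349; 10 × 0.10 × 0.9^9 = 0.387; sum 0.736.

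| Assumed severe share | Expected of 10 | None of 10 | At most one of 10 | Expected of 20 | None of 20 | At most one of 20 |
|---|---|---|---|---|---|---|
| 5% | 0.5 | 60% | 91% | 1 | 36% | 74% |
| 10% | 1 | 35% | 74% | 2 | 12% | 39% |
| 20% | 2 | 11% | 38% | 4 | 1% | 7% |
| 33% | 3.3 | 2% | 10% | 6.7 | <0.1% | 0.3% |

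**Step 2: does stratified enrollment settle it?** Suppose a share s of enrolled adults is severe, and severe adults qualify and volunteer at u times the rate of the others. Then p = s·u / (s·u + 1 − s). With s = 1/3 and u = 1/2, p = 0.167 / (0.167 + 0.667) = 20%. With u = 1/4, p = 0.083 / (0.083 + 0.667) = 11%. So even equal thirds at enrollment can lead to the 20% or 10% rows. The values of s and u are assumptions.

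**Step 3: what one severe participant allows.** The protocol's two-group test is the Wilcoxon rank sum test at two-sided 5% (Sections 7.2.1 and 7.4.2). Its smallest attainable exact p-value is 2 / C(n1 + n2, n1). For 1 against 9 this is 2/10 = 0.20, and for 1 against 19 it is 2/20 = 0.10. Neither can reach 0.05. Descriptively, one person shows no within-group variation.

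**Step 4: what reserved places would give.**
- 10 places over three levels (3/3/4): smallest p is 2/20 = 0.10 for 3 against 3, and 2/35 = 0.057 for 3 against 4. No pairwise test can reach 0.05.
- 20 places over three levels (6/7/7): 2/1716 = 0.0012 for 6 against 7.
- 10 places over two levels (5/5): 2/252 = 0.008.

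Reserved places protect representation. They do not turn the subset into a powered comparison.

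**The case against.** The case on the other side is substantial, and much of it stands.

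- **A reader might infer that severe cases are excluded by the outpatient rule.** They are not. The rule applies on the day of the procedure, while severity is the worst level of care received. An ICU survivor discharged in time can qualify.
- **A reader might infer that the bank closes at DPO 90.** It does not. The window belongs to each participant, and enrollment is estimated at 2 years, so new adults keep entering it. What closes the subset is the 10-20 limit.
- **A reader might assume that mild cases volunteer first.** The protocol says nothing about the order of volunteering by severity. That the criteria thin the severe group is a plausible inference and no more.
- **Enrollment is stratified and meant to span the disease spectrum.** If that carried through to volunteers at about one third per level, the risk would be small with 20 places. It is not guaranteed to carry through.
- **Few ICU survivors would not end every comparison.** Section 5.1 asks for variable severity and does not require an ICU group. A hospitalized versus never-hospitalized comparison could survive.
- **The stakes are limited.** The objective is exploratory, the study is sized on feasibility, and the primary T-cell and B-cell objectives rest on the scheduled Group 1 blood draws. The comparison with vaccine recipients does not depend on severity balance.

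The Manual of Procedures is not at hand and might contain a selection rule. If so, it would conflict with Section 4 as written.

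**Conclusion.** The point holds in a limited form. The filling rule in Section 4 has no severity element and can defeat a purpose stated in Section 5.1, and neither section explains how the donors in Table 1 are selected. The size of the risk depends on a severe share that the protocol does not give. Over an assumed 5% to 33%, the chance of at most one former ICU participant runs from 91% down to 10% with 10 places, and from 74% down to 0.3% with 20. It is a serious risk at 10 places unless the share is near one third, and a minor one at 20 places once the share reaches about 20%. These figures assume independent volunteers and count only ICU care as severe.

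The protocol does not support the stronger conclusion that the study's severity analyses are compromised. The effect is confined to one exploratory subset. It is still worth correcting before activation, because places already used cannot be given to later severe participants.

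**What to change.** In Sections 4 and 5.1, replace acceptance in order of volunteering with places reserved across the severity strata used for Group 1 enrollment, for example highest level of care, or at least hospitalized versus never hospitalized. State a date after which unfilled places are released to any eligible volunteer. Tying the reservation to the enrollment strata suits a template for an unknown pathogen better than fixed thirds by care level. Align the word selected in Table 1 with this rule. If the sponsor prefers to keep the present rule, remove severity comparison as a purpose of the subset in Section 5.1.

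The leukapheresis eligibility criteria stay as they are. The cost is a sentence or two and a running tally of places across sites. The drawback is that the places may fill more slowly. The subset should still be described as exploratory and descriptive, particularly if only 10 places are used.

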5. STUDY POPULATION

5.1 Selection of the Study Population

Up to 1,000 male and female participants, adults ≥ 18 years of age and children < 18 years of age, will be screened to enroll participants who meet all eligibility criteria and agree to participate.

Patients will be recruited from 10 VTEU sites and/or their sub-sites. Sites can enroll from either outpatient or inpatient sites, or both. Enrollment will be stratified by disease severity or other major categories of disease presentation as applicable. Pregnant women will not be excluded from enrollment. Blood collection volumes will be adjusted accordingly for these participants. There will not be a required sample size for this population. As this study is a descriptive study, sample size is based on feasibility instead of power for hypothesis testing.

- Group 1: Patients with confirmed or suspected Pathogen “X” infection, and
- Group 2: Close contacts of patients with confirmed and/or suspected Pathogen “X” infection enrolled in Group 1.

A subset of 10-20 adult volunteers from Group 1 will undergo leukapheresis during follow-up to compare immunological responses in those with variable severity and also to allow future comparisons with those receiving Pathogen “X” vaccines (enrolled in other studies). Study staff will inform potential participants/legally authorized representatives (LAR) of the study, obtain informed consent, and determine study eligibility. Individuals who meet all study eligibility criteria and agree to participate will be enrolled.

Usual clinical management at VTEU outpatient or inpatient sites, including standard medical care and standard therapy, will not be modified because of the study. All participants will receive appropriate treatment for Pathogen “X” that is accepted by medical experts as standard of care for the specific institution and is widely used by healthcare professionals.

5.2 Inclusion/Exclusion Criteria

5.2.1 Subject Inclusion Criteria

Subjects must meet all the following inclusion criteria to be eligible to participate in the study:

- Must provide informed consent or have a LAR who provides informed consent.
 - Must be available and willing to participate for the duration of this trial.
 - Possible or definitive Pathogen “X” infection, or close contacts of patients with possible or definitive Pathogen “X” infection.
-

5.2.2 Leukapheresis Inclusion Criteria

A subject must meet all the following criteria to be eligible for leukapheresis:

- Written informed consent for leukapheresis is provided.
- Age ≥ 18 years old.
- Weight ≥ 110 pounds.
- Screening laboratory (e.g., Hgb) and clinical (e.g., pulse, blood pressure) evaluations are within acceptable normal reference ranges at the site where the leukapheresis procedure will be performed.
- Negative urine or serum pregnancy test within 48 hours of the leukapheresis procedure for women of childbearing potential.
- Adequate bilateral antecubital venous access.
- No use of blood thinners, aspirin or NSAIDs at least 5 days before the leukapheresis procedure.
- Must be an outpatient at time of leukapheresis procedure.
- The investigator deems the participant is medically stable to undergo the leukapheresis procedure.

5.2.3 Subject Exclusion Criteria

Subjects meeting any of the following criteria at baseline will be excluded from study participation:

- The investigator feels, for any reason, that participation in the study is unsafe for the patient or inappropriate for achievement of the study objectives.
- Anticipated mortality within 24 hours of enrollment.
- Receipt of intravenous immunoglobulin (IVIG), plasma, or monoclonal antibody directed against Pathogen “X”.
- Receipt of an investigational immunomodulator or enrollment in a treatment trial that includes potential randomization to receive an investigational immunomodulator (e.g., baricitinib, anakinra, sarilumab, siltuximab, tocilizumab, interferon).²
- Prior or current participation in a Pathogen “X” vaccine clinical trial.

² This does not include steroids (e.g., prednisone, dexamethasone, solumedrol) or antivirals (e.g., remdesivir, lopinivir/ritonavir).

- Patients with immunosuppressive conditions (e.g., uncontrolled HIV defined as stable CD4 <400 and/or viral load >1,000 within 3 months of enrollment, solid organ transplant, active cancer treatment).

5.3 Reasons for Withdrawal

Participants may voluntarily withdraw their consent for further study participation at any time and for any reason without penalty or prejudice to future medical care. Participants may be withdrawn from further study participation for the following reasons:

- Medical disease or condition, or any new clinical finding for which continued participation, in the opinion of the site principal investigator (PI) or appropriate sub-investigator, would compromise the safety of the participant, interfere with the participant's successful completion of the trial, or interfere with the evaluation of responses.
- As deemed necessary by the site PI or appropriate sub-investigator for noncompliance or other reason.
- Termination of the study.

5.3.1 Handling of Withdrawals

Participants who withdraw their consent from further study participation will not continue any study procedures and will no longer be contacted for follow-up. Participants who are withdrawn from further study participation by the site PI or appropriate sub-investigator for any reason will not continue study procedures.

If participants fail to appear for a follow-up visit, extensive effort (e.g., three documented contact attempts via phone calls or emails, made on separate occasions and followed by a certified letter) will be made to locate or recall them or at least to determine their health status. Subjects who cannot be located after extensive effort will no longer be contacted for follow-up. These efforts will be documented in the subject's records.

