3. OBJECTIVES

3.1 Study Objectives Endpoints (Outcome Measures)

Table 1: Objectives and Endpoints (Outcome Measures)

Objectives	Endpoints
Primary	

 To characterize Pathogen “X” binding and neutralizing antibody responses by age and disease severity in study subjects 	
 Pathogen “X” neutralization assay (e.g., PRNT, FRNT) Pathogen “X” pseudoneutralization assay

 To characterize T cell responses by age and disease severity 	
 T cell ELISpot and/or ICS assays

 To characterize B cell responses by age and disease severity 	
 Memory B cell testing Plasmablast antibody secreting cells (ASCs) responses

 To describe the clinical presentation and outcomes of Pathogen “X” infection in study subjects 	
 Clinical symptoms, laboratory abnormalities, days of illness, residual clinical problems, survival/death
Secondary	

 To describe innate immune responses to Pathogen “X” 	
 Transcriptomics, flow cytometry, serum and/or culture supernatant cytokine ELISA

 To collect specimens for isolation of Pathogen “X” from body compartments pertinent to the pathogen 	
 PCR and/or cultures

 To determine rates of Pathogen “X” infection among close contacts of infected patients enrolled in Group 1 	
 Rates of Pathogen “X” detection among close contacts of infected enrolled subjects at enrollment and over follow-up

 To determine the persistence of Pathogen “X” in whole blood, serum, urine, saliva, stool, or other body fluids as available (e.g., semen, vaginal secretions, breast milk) and characterize modes of pathogen shedding to support the development of diagnostic assays and public health prevention policy around transmission risk 	
 Repeated PCR and/or cultures

Objectives	Endpoints
Exploratory	

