6.1.2 Follow-up Visits

At intervals determined by the biologic characteristics of Pathogen “X” after enrollment (up to 12 months)

Participants will undergo the following procedures as necessary:

- Collection of patient information including interval medical history, medications, and medical record review if available
- Collection of signs and symptoms of Pathogen “X” infection
- Review contact information
- Physical exam may be performed to assess the need for advanced care in participants
- Vital signs may be collected as necessary
- Collection of specimens from body compartment specific to Pathogen “X”
- Collection of residuals from standard of care specimens (if available)

Participants will have the following biological specimens collected as necessary:

- Specimens from body compartment specific to Pathogen “X”
- 10mL blood for serum from adults
- 2.5mL blood for serum from children
- 24mL blood for PBMCs from adults with significant anemia (Hgb<10), compromised cardiac output and/or significant respiratory compromise
- 60mL blood for PBMCs from adults without significant anemia (Hgb≥10) and without compromised cardiopulmonary functions
- Pediatric blood volumes for PBMCs will total ≤1 mL/kg; see MOP for specific details.

⁴ Including blood, sputum, endotracheal aspirates, bronchoalveolar lavage and saliva

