7. STATISTICAL CONSIDERATIONS

7.1 Study Hypotheses and Design

The overall objective of this prospective observational cohort study is to characterize the natural history and immune responses to Pathogen “X” infection in patients who present varying levels of disease severity and clinical symptoms, and in their close contacts. The study hypothesizes that Pathogen “X” elicits broad immune responses in individual patients, and that these responses vary over time during infection and as disease severity and symptoms progress. The study will determine whether immune responses associated with disease severity, symptoms, and demographic variables. In particular, it will focus on association with age, and consider other known or suspected factors that associate with immune responses (e.g., sex). It will also characterize spread of infection among close contacts of Pathogen “X” infected patients.

To address its objectives with adequate power, the study will target enrolling approximately 1,000 Pathogen “X” infected or suspected children and/or adult patients (Group 1) and children and/or adult close contacts of the Pathogen “X” infected patients who are enrolled in Group 1 (Group 2). Participants in Group 1 will be representative of the Pathogen “X” disease spectrum.

The primary statistical analysis of data from participants enrolled in Group 1 will be conducted using the most severe level of care (hospitalized ICU, hospitalized non-ICU, outpatients not hospitalized) received by each study participant. Secondary statistical analyses will be performed using additional disease severity scales if developed (see Appendix B).

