 17. Holm S. A Simple Sequentially Rejective Multiple Test Procedure. *Scandinavian Journal of Statistics.* 1979;6(2):65-70.

APPENDIX A: SCHEDULE OF EVENTS (SOE)**Table 2: Group 1 Pathogen “X” Suspected or Confirmed Cases SOE**

Procedures	Screening/ Enrollment/ Baseline Visit 1, Day 1	FUP Visit 2 ¹ DPO 7	FUP Visit 3 ¹ DPO 15	FUP Visit 4 ¹ DPO 30	FUP Visit 5 ¹ DPO 90	Optional Study Visit (between DPO 30 & 90)	Study Visit 7 ¹ DPO 180	Final Visit 8 ¹ DPO 365
Informed consent	X							
Review Inclusion/Exclusion Criteria	X							
Demographics and Sociodemographics	X							
Medical history/Exposure history	X							
Medications	X	X	X	X	X		X	X
Signs/Symptoms of Pathogen “X” infection	X	X	X	X	X			
Contact Information ²	X	(X)	(X)	(X)	(X)	(X)	(X)	(X)
Interval History Updates		X	X	X	X		X	X
Review of medical records	(X)	(X)	(X)	(X)	(X)		(X)	(X)
Physical exam	(X)	(X)	(X)	(X)	(X)		(X)	(X)
Vital signs ³	(X)	(X)	(X)	(X)	(X)			
Height and weight ⁴	X							
Collection of specimens ⁵	X	(X)	(X)	(X)	(X)		(X)	(X)
Phlebotomy for serum, adults (mL)	10		10	10	10		10	10
Phlebotomy for serum, children (mL)	2.5			2.5	2.5			2.5 ⁶

Procedures	Screening/ Enrollment/ Baseline Visit 1, Day 1	FUP Visit 2 ¹ DPO 7	FUP Visit 3 ¹ DPO 15	FUP Visit 4 ¹ DPO 30	FUP Visit 5 ¹ DPO 90	Optional Study Visit (between DPO 30 & 90)	Study Visit 7 ¹ DPO 180	Final Visit 8 ¹ DPO 365
Phlebotomy volumes for PBMCs in adults (mL)	24 ⁷ or 60 ⁸		8 or 16 mL	24 ⁷ or 60 ⁸	24 ⁷ or 60 ⁸		24 ⁷ or 60 ⁸	60
Phlebotomy volumes for PBMCs in children (mL)	<1 mL/kg ⁹		<1mL/kg	<1 mL/kg ⁹	<1 mL/kg ⁹			<1 mL/kg ^{6,9}
Collect residuals from standard of care ¹⁰	X	X	X	X	X			
Leukapheresis [subset of adult patients] ^{11, 12}						5x10 ⁸ to 1x10 ¹⁰ cells		
Per Visit Blood Volume Total, adults (mL)	34 ⁷ or 70 ⁸		10	34 ⁷ or 70 ⁸	34 ⁷ or 70 ⁸		34 ⁷ or 70 ⁸	70
Running Blood Volume Total, adults (mL)	34 ⁷ or 70 ⁸		44 ⁷ or 80 ⁸	78 ⁷ or 150 ⁸	112 ⁷ or 220 ⁸		146 ⁷ or 290 ⁸	216 ⁷ or 360 ⁸
Per Visit Blood Volume Total, children (mL)	2.5 + PBMC			2.5 + PBMC	2.5 + PBMC			2.5 + PBMC
Running Blood Volume Total, children (mL)	2.5 + PBMC			5 + PBMC	7.5 + PBMC			10 + PBMC

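### Section 5.3.1 ends all study procedures, which as listed include medical record review, for anyone the investigator withdraws, so deaths and rises in level of care after withdrawal go uncollected even when consent stands

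*Protocol*

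**What the plan says.** - **Grounds for withdrawal (Protocol 5.3).** The site investigator may withdraw a participant for a medical condition or new clinical finding if continuing would compromise safety, interfere with completing the study, or interfere with evaluating responses.
- **Consequence (Protocol 5.3.1).** "Participants who are withdrawn from further study participation by the site PI or appropriate sub-investigator for any reason will not continue study procedures". Nothing is excepted for vital status, outcome or passive follow-up. Participants who withdraw consent have a separate rule: they "will not continue any study procedures and will no longer be contacted for follow-up".
- **Missed visits (Protocol 5.3.1).** Sites must make extensive efforts to recall participants who miss a visit, or at least to establish their health status. Nothing similar is stated for participants whom the investigator withdraws.
- **What counts as a procedure.** The follow-up procedures in Protocol 6.1.2 include "Collection of patient information including interval medical history, medications, and medical record review if available". The Procedures column of Appendix A, Table 2 has a row "Review of medical records".
- **What has to be observed.** The primary clinical endpoint in Table 1 is "Clinical symptoms, laboratory abnormalities, days of illness, residual clinical problems, survival/death". Section 7.1 bases the primary Group 1 analysis on severity defined "using the most severe level of care (hospitalized ICU, hospitalized non-ICU, outpatients not hospitalized) received by each study participant". Section 6.3 has Group 1 severity evaluated until symptoms resolve and scored at the highest level reached.

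**The concern.** One of the grounds for withdrawal is a change in clinical state, and clinical state is what the study sets out to describe. Reading records carries no physical risk, and a participant withdrawn by the investigator has not necessarily withdrawn consent. Stopping record review along with visits and sampling therefore gives up outcome data for no evident protective reason.

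The loss would not be random with respect to illness. If someone is withdrawn while worsening, a later ICU admission, death or residual problem is not captured. This is a rule about data collection, so an analysis plan cannot recover what the sites were told to stop recording.

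**Working it through.** The protocol has no figure to reproduce. Its precision and power tables in Section 7.2 are unfilled, and the 15% missing-data allowance there covers immunological assays only. The check is therefore textual, with an illustration of scale.

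**Step 1: does record review stop?** Section 5.3.1 ends study procedures. Section 6.1.2 and Appendix A, Table 2 both list record review as a procedure. Taken together, it stops. This is an inference from the listing, because Section 5.3.1 does not name record review.

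**Step 2: can the passages all be followed?** Take a Group 1 participant withdrawn while still symptomatic. Section 6.3 requires severity to be evaluated until symptoms resolve, and Section 5.3.1 ends the procedures by which it would be evaluated. Both cannot be followed. Section 7.1 needs the maximum level of care received, which is not known if later care is not looked up.

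**Step 3: direction.** Peak level of care is a maximum over time. For each participant, the maximum up to withdrawal is at most the maximum over full follow-up, so any error in peak severity is toward milder disease. A death after withdrawal is either missed or drops out with the participant.

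**Step 4: scale (all inputs assumed).** Let N = 500 in Group 1, true peak-ICU proportion p_ICU = 20% and true mortality 10%, with all deaths among ICU-peak patients. Let w be the share of ICU-bound patients, and the same share of deaths, withdrawn before the event is recorded.

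- Withdrawn participants kept in the denominator: observed = p(1 − w).
- Withdrawn participants excluded: observed = p(1 − w)/(1 − p_ICU·w).
- 95% half-width = 1.96·√(p(1 − p)/N). ICU: 1.96·√(0.20·0.80/500) = 3.5 points. Death: 1.96·√(0.10·0.90/500) = 2.6 points.

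| w | ICU kept | ICU excluded | Death kept | Death excluded |
|---|---|---|---|---|
| 5% | 19.0% | 19.2% | 9.5% | 9.6% |
| 10% | 18.0% | 18.4% | 9.0% | 9.2% |
| 20% | 16.0% | 16.7% | 8.0% | 8.3% |
| 30% | 14.0% | 14.9% | 7.0% | 7.4% |

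Example for w = 20%: ICU kept 0.20·0.80 = 0.160; ICU excluded 0.160/(1 − 0.20·0.20) = 0.160/0.96 = 0.167. In patients, 500·0.20 = 100 are ICU-bound, so w = 5% is 5 people and w = 20% is 20 people.

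**Step 5: compare with sampling error.** The same formulas were run for ICU 10% with death 3% (half-widths 2.6 and 1.5 points) and for ICU 30% with death 15% (4.0 and 3.1 points).

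- w up to 10%: every shift lies inside the half-width in all three scenarios.
- w = 20%: death shifts stay inside (middle scenario with withdrawn kept, 2.0 against 2.6). The ICU shift exceeds the half-width in the middle scenario with withdrawn kept (20.0 − 16.0 = 4.0 against 3.5) but not excluded (3.3). It exceeds it both ways in the high scenario (6.0 and 4.5 against 4.0).
- w = 30%: the ICU shift exceeds the half-width in every scenario. The death shift does so in the middle scenario with withdrawn kept (3.0 against 2.6) and both ways in the high scenario (4.5 and 3.5 against 3.1).

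Every shift is toward milder disease.

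**The case against.** The strongest reply is that such withdrawals should be rare. The study is noninterventional, ICU patients are an intended stratum, and Section 5.3 is permissive: worsening alone does not meet it, because continuing participation must itself be the problem. Section 6.4.1 already provides for low hemoglobin, cardiogenic shock and severe hypoxemia by reducing PBMC volume, and lets the draw be omitted on clinical judgment while the participant stays enrolled. This stands and is why the effect is probably modest. It does not remove the point: Section 6.4.1 names visits 1, 5 and 7 only, and it does not touch withdrawal on the ground of interference with evaluating responses.

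A second reply is that Section 5.3.1 applies its no-contact clause only to consent withdrawal, so passive follow-up after investigator withdrawal may have been intended. That is possible, and the MOP or consent form, neither available for this check, might say so. The protocol does not, and sites could read it differently.

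Two stronger readings are tempting but unsupported. A reader might infer that someone withdrawn at ICU transfer would be analysed as non-ICU. Section 7.1 uses the highest level received and Section 7.4 analyses all data from enrolled patients, so a level reached by withdrawal is kept; only later events are lost. A reader might also infer that the missing-at-random methods in Section 7.4.2 must fail. If recorded deterioration triggers withdrawal, missingness can depend on observed data, which that assumption permits. It fails only if the unseen later course matters beyond what was recorded.

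**Conclusion.** The point holds in conditional form. Read together, Sections 5.3.1, 6.1.2 and Appendix A, Table 2 stop outcome collection after investigator withdrawal, and this conflicts with Sections 6.3 and 7.1 for anyone withdrawn while ill. To the extent such withdrawals occur, mortality and peak severity are understated.

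The documents do not show that the description is biased by any particular amount. Under the assumed inputs, the shift is within sampling error when up to 10% of ICU-bound patients are withdrawn before the event. It starts to exceed sampling error for ICU at about 20%, and for death at about 30% in the middle and high scenarios. Given Section 6.4.1, the lower end is more plausible, though the protocol offers no rate to confirm that. This is a cheap improvement worth making before the protocol is activated, not a flaw that undermines the study.

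**What to change.** Reconcile Section 5.3.1 with Sections 6.3 and 7.1:

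- State that withdrawal by the investigator ends study visits and specimen collection only.
- State that vital status, outcome and highest level of care continue to be taken from medical records through DPO 365, unless the participant or LAR withdraws consent for this.
- Record on the CRF the reason for withdrawal, and whether sampling only or all data collection stopped.

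The cost is a short edit to Section 5.3.1, one consent-form sentence covering continued record access, the CRF entries, and a little record-review work for what should be few participants. Where records are unavailable some outcomes will still be missing, but the recorded reason will let the analysts see how many and why.
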